research protocol, that is, pretest (week 1), intermediate test 1 (week 6), test intermediate 2 (week 11) and posttest (week 16). Likewise, the groups formed randomly and the confrontation between them determined by chance at all test will be respected. If for any reason a participant cannot take the test due to any circumstance (absence at the session, physical discomfort, momentary bruises, injury or unexpected situations), his replacement will be arranged with IUEFD student with experience as soccer players and who previously know the protocol to complete the gap, or with soccer players who are on trial at the club and who are not part of the comparison groups. The tests will be carried out on Wednesday from 6 to 8 in the morning in the respective weeks (1, 6, 11 and 16).

Once the tests have been completed and duly filmed, the respective videos will be passed on to the evaluator (video analyst) who will download the videos, analyze the different actions and behaviors developed by each of the participants through the LINCE PLUS video analysis software and record the data in Excel files in the database created for this purpose. This database will be created in such a way that a code is generated for the participants and no one can identify who the information registered and consigned there corresponds to (except the main researcher) who will save it on their personal computer, on a hard drive to keep copy and in the cloud. These files will be kept with a password, which only the principal researcher will know.

The information and data resulting from the respective analyzes carried out by the evaluator will be sent to the statistician who will proceed to carry out the respective analysis and application of tests in accordance with the data treatment that appears in the data analysis section.

Prior to carrying out the FOCOS test that evaluates the primary and secondary outcomes and, prior to the execution of the tests that evaluate executive functions (exploratory outcome), the following question will be asked to the participants: from 0 to 100, ¿How mentally fatigued are you? Being 0 (not at all fatigued) and 100 (maximum fatigue).

The evaluations of week 1 were carried out on two different days and in the following order: the first day the survey was carried out, mass, height, mental fatigue and finally, the tests were applied to assess the executive functions, for which participants were

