summoned by groups of 4 every hour. Total application time from full battery was approximately 60 minutes. On the second day, the FOCOS field test was carried out and all the participants were summoned at 6 in the morning. In the intermediate tests 1 (week 6) and 2 (week 11) only the evaluations will be carried out through FOCOS. Finally, the post-test evaluations (week 16) will be carried out in the same way as in the pre-test, that is, they will be carried out on two different days and in the following order: the first day the tests will be applied to assess the executive functions and mental fatigue, on the second day, the field test (FOCOS) will be carried out, for which all the participants will be summoned at 6 in the morning.

Bias Control

To control biases in the different stages of the study (planning, execution, and data analysis), different strategies and actions were established to obtain reliable results. Bias control was carried out as follows:

Control of Allocation Biases (Randomization Biases)

To avoid these biases, the participants were randomized to two comparison groups (GE and CG) as previously described in the randomization process.

Control of Information Biases (Systematic Biases)

To avoid these biases, reliable and valid protocols and tests are used, in addition, the evaluation protocols were standardized (pretest, intermediate test 1, intermediate test 2 and posttest), which will be carried out under similar conditions, with the same equipment and by the same evaluators). In the same way, the equipment and instruments were calibrated in accordance with quality norms and standards. It is important to mention that the personnel that carry out the evaluations and interventions are experts in their respective areas and that those necessary for the development of a protocol or intervention were trained. In addition, the evaluator of the actions related to the PTK and the IE (offensive, defensive, and global) must demonstrate and achieve a good stability, which will be obtained and calculated through test-retest, once the evaluator achieves a score for above 0.6 the PTK evaluation process will continue in the research.

Confounding Bias Control

To avoid these biases, confounding variables (age, sporting age, playing position, socioeconomic status, educational level, mass, BMI, and mental fatigue) will be controlled.

The study has masking (blinding) at two levels (assessments and data analysis).

Analysis of data

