To establish the distribution of the data of the quantitative variables, the Shapiro-Wilk test will be applied. The variables that present a normal distribution will be summarized with means and standard deviation. Variables that present a non-normal distribution will be summarized with medians and interquartile ranges. Likewise, the qualitative variables will be presented in absolute and relative frequency tables.

To establish the behavior of the offensive, defensive, and global IE, a repeated measures design will be carried out that includes 4 evaluations over time (pretest, intermediate test 1, intermediate test 2 and posttest). For this, an ANOVA of repeated measures or the Friedman test will be used according to the normality of the variables, in addition, the assumption of homogeneity of the variances will be evaluated based on the Levene statistic. Since different dependent variables will be evaluated, a multivariate analysis of variance (MANOVA) will also be performed.

For the variables related to executive functions, an intragroup analysis of each of the groups (GE and GC) will be carried out, comparing the pretest and posttest values to establish possible differences, for which the dependent student t test or the Wilcoxon test of according to its distribution. In addition, an intergroup analysis will be carried out to compare the possible differences between the groups (GE and GC), for which the student t test for independent samples or the Mann Whitney U test will be applied according to the distribution of the variables. Similarly, confidence intervals (CI95) and two-tailed effect sizes will be reported, with alpha (α) set to 0.05 and statistical power 0.8 (1- β). The statistical significance value is set at $p \leq 0.05$. An analysis of the information will be carried out using the statistical package SPSS version 27 and the software R free version 4.0. Procedures will be carried out to detect possible inconsistencies in the measurements and to identify outliers and extreme values. Likewise, if necessary, statistical adjustments will be made. Intention-to-treat analysis will be performed.

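### Executive functions (exploratory): the between-group test has no pretest covariate and does not say whether posttest or change is compared; ANCOVA on the pretest would be more precise if pretest and posttest correlate above about 0.2

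*Combined protocol and SAP*

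**What the plan says.** The Analysis of data section gives executive functions two analyses. Within each group there is a paired analysis, "comparing the pretest and posttest values to establish possible differences, for which the dependent student t test or the Wilcoxon test". Then "an intergroup analysis will be carried out to compare the possible differences between the groups (GE and GC". The method named in the plan for this second analysis is a simple two-sample test: "the student t test for independent samples or the Mann Whitney U test will be applied according to the distribution of the variables". The same section promises that "confidence intervals (CI95) and two-tailed effect sizes will be reported".

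The pretest is available for every score. The Executive functions section has the whole battery given before and after the interventions. Data Collection Procedures confirms that "the post-test evaluations (week 16) will be carried out in the same way as in the pre-test". That section also sets the status of these outcomes, in the sentence on the mental-fatigue question asked "prior to the execution of the tests that evaluate executive functions (exploratory outcome".

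Two other statements might have supplied a baseline adjustment, but neither does. Confounding Bias Control says that "confounding variables (age, sporting age, playing position, socioeconomic status, educational level, mass, BMI, and mental fatigue) will be controlled", a list without the executive-function pretest. The Analysis of data section adds that "if necessary, statistical adjustments will be made", without naming a variable or a model. The repeated-measures ANOVA or Friedman test is planned for the offensive, defensive and global effectiveness indices, not for executive functions.

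**The concern.** The trial has 24 players and was not sized on executive functions, yet the effect on them is a stated objective and is in the title. In so small a trial a player's own pretest is likely to be the best available predictor of his posttest, and it is already collected. A posttest comparison ignores it. A change-score comparison uses it, but with its coefficient fixed at 1. ANCOVA estimates that coefficient.

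The text also leaves open which of the two quantities is compared. The plan uses the same phrase about possible differences for the pre-post contrast and for the group contrast. That may point to change scores but does not settle it. At stake are the width of the intervals for these outcomes and a choice that should be fixed before the data are seen. The PTK conclusions and the sample size are not affected.

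**Working it through.** **The plan's own figure first.** Sample Size Calculation gives a difference of 1.13 and an SD of 0.81, so d = 1.13/0.81 = 1.395. With 12 per group, two-sided alpha 0.05 and 22 df, the noncentrality is 1.395 × √(12/2) = 3.42 and exact power is 90.4%. The same method gives 10, 11, 12, 15 and 20 per group for the five scenarios, as stated. The stated 24 is therefore reproduced. Nothing in the plan links this effect to executive functions.

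**Inputs for the comparison.** From the documents: 12 per group (N = 24), 1:1 allocation, two-sided alpha 0.05. Assumed, because the documents give no values: pre-post correlation r, equal variances before and after, normal scores, and true effects of 1.0 and 0.5 posttest SD.

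**Variance of the group difference, relative to a posttest comparison:**
- posttest only: 1
- change score: 2(1 − r)
- ANCOVA: (1 − r²) × [1 + 1/(N − 4)] = (1 − r²) × 1.05, where 1.05 is the price of estimating the slope

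Residual df are 22 for the t tests and 21 for ANCOVA; the critical values are 2.0739 and 2.0796. Example at r = 0.5: 0.75 × 1.05 = 0.788, so the CI width ratio to posttest is √0.788 × 2.0796/2.0739 = 0.890.

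| r | ANCOVA variance | Change variance | CI width, ANCOVA/posttest | CI width, ANCOVA/change |
|---|---|---|---|---|
| 0 | 1.05 | 2.00 | 1.028 | 0.727 |
| 0.3 | 0.956 | 1.40 | 0.980 | 0.828 |
| 0.5 | 0.788 | 1.00 | 0.890 | 0.890 |
| 0.7 | 0.536 | 0.60 | 0.734 | 0.947 |
| 0.8 | 0.378 | 0.40 | 0.617 | 0.975 |

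A simulation of 40,000 trials at each of r = 0, 0.3, 0.5 and 0.7 gave ANCOVA variance ratios of 1.048, 0.959, 0.785 and 0.534, in agreement.

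**Break-even points.**
- Against posttest, on variance: (1 − r²) × 1.05 < 1 requires r² > 1 − 1/1.05 = 0.0476, so r > 0.22. On CI width, which includes the lost df, it is r > 0.23.
- Against change, on CI width: (1 + r) × 1.05 × (2.0796/2.0739)² < 2, that is 1 + r < 2/1.0558 = 1.894, so r < 0.89.

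**Power at 12 per group** (exact noncentral t for the two t tests; 200,000 simulated trials per cell for ANCOVA):

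| True effect | r | Posttest | Change | ANCOVA |
|---|---|---|---|---|
| 1.0 SD | 0 | 65% | 38% | 63% |
| 1.0 SD | 0.3 | 65% | 51% | 67% |
| 1.0 SD | 0.5 | 65% | 65% | 75% |
| 1.0 SD | 0.7 | 65% | 86% | 89% |
| 0.5 SD | 0.3 | 22% | 17% | 22% |
| 0.5 SD | 0.5 | 22% | 22% | 26% |
| 0.5 SD | 0.7 | 22% | 33% | 36% |

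With no true effect, ANCOVA rejects in 4.9 to 5.0% of simulated trials, so the gain is not bought with type I error.

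**The case against.** The strongest reply is that the planned test is valid, the outcomes are exploratory, and the choice between sound methods belongs to the trial team. That stands, and it sets the weight of the point.

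The gain is also conditional. Below r of about 0.2 ANCOVA is slightly worse than a posttest comparison: at r = 0 its interval is about 3% wider. If change scores are meant, the plan already uses the pretest, and the gain at r = 0.7 and 1.0 SD is only 3 points. At 0.5 SD the gains at r = 0.3/0.5/0.7 are about 1/5/14 points over posttest and 6/5/3 over change, and power never passes 36%. All of this stands. It does not remove the point, because the possible loss is small and the possible gain is material over a wide range of r.

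A reader might infer more than the documents support:
- That the planned comparison is biased or invalid. It is not: randomisation protects it whether posttest or change is compared.
- That conclusions will rest on the separate within-group tests. The plan does not say so, and it provides a between-group analysis with intervals.
- That all eight listed confounders will enter one model and use up the degrees of freedom. The plan states no such model.

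**Conclusion.** The point holds as an optional improvement in precision, together with a clarification of what is compared. The plan has no pretest covariate for executive functions, and neither the confounder list nor the clause on adjustments supplies one. At 12 per group and r = 0.5, ANCOVA narrows the interval by 11% against either reading of the plan and raises power at 1.0 SD from 65% to 75%. At r = 0.7 the interval is 27% narrower than for posttest and 5% narrower than for change.

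These sizes rest on assumed correlations, normal scores and assumed effects, none of which the documents give. ANCOVA does not make the executive-function analysis well powered for moderate effects.

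**What to change.** In the Analysis of data section, make the between-group comparison for each executive-function score an ANCOVA of the posttest on group, with that score's own pretest as covariate. Report the adjusted difference with its 95% CI, label it exploratory, and name it as the analysis on which between-group conclusions rest. This also settles the choice between posttest and change. Where residuals are likely to be clearly skewed, as completion times may be, specify a transformation such as the log in advance. Make the change before the group codes are opened to the analyst.

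The cost is a short addition to the SAP, one degree of freedom per model (22 to 21), and a small variance penalty if r is near 0 (about 2 points of power at 1.0 SD). Any transformation for the timed scores has to be named beforehand. No new data are needed, and ANCOVA can be fitted in the SPSS and R software that the plan already names.

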
Players with musculoskeletal disorders at the time of sample selection.

Players recovering from injury.

Sample Size Calculation

A systematic probabilistic sampling of permuted blocks was carried out, for which the Epidat software, V. 4.2, was used. Taking into account the study by Sierra-Ríos et al., (2020) in which they report a mean difference of 1.13 and a standard deviation of 0.81, 5 scenarios were established to calculate the sample size (with powers of 80, 85, 90, 95 and 99%). Based on these five scenarios, the samples found are:

Scenario 1 (80% power): (20 soccer players. GE = 10 and GC = 10).

Scenario 2 (85% power): (22 soccer players. GE = 11 and GC = 11).

Scenario 3 (90% power): (24 soccer players. GE = 12 and GC = 12).

Scenario 4 (95% power): (30 soccer players. GE = 15 and GC = 15).

Scenario 5 (99% power): (40 soccer players. GE = 20 and GC = 20).

Based on these results of the calculation of different sample sizes, it decided to work with scenario 3 described above.

Randomization Process

To carry out the randomization sequence generation method, a sequence of permuted blocks of 4, 6 was generated. The relationship between groups is 1:1, for which the random assignment software (simulation) was used <https://www.sealedenvelope.com/simple-randomiser/v1/lists>.

The allocation was concealed by means of sealed and opaque envelopes, for which the 24 envelopes were available for each one of the participants. The envelopes were numbered from 1 to 24, the name of each research participant was added to them along with a sheet of carbon paper and the name of each research participant was marked for each intervention experimental group (GE) and control group (GC). This process of randomization sequence generation, allocation concealment, and allocation was performed by someone other than the research staff.

Variables

The study's variables, their operationalization, function, nature, measurement scales, units of measurement and instruments used are described in Table 1.

Table 1. Variables and their operationalization

Variable	Function	Nature	Scale	Unit of measurement/values	Instrument
PTK (Offensive IE)	Dependent	Quantitative	Discrete, interval Continuos, Ratio	Volumen (N° of times the action is performed) IE (*formula)	FOCOS
PTK (IE Defensive)	Dependent	Quantitative	Discrete, interval Continuos, Ratio	Volumen N° of times the action is performed) IE (**formula)	FOCOS

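### Intention-to-treat is stated, but the tests named for the IE outcomes would, in standard form, drop any player who misses one FOCOS test, and no method for missing scores is given

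*Combined protocol and SAP*

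**What the plan says.** All references are to the combined protocol and SAP.

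- **Analysis of data, IE outcomes.** A "repeated measures design will be carried out that includes 4 evaluations over time" (weeks 1, 6, 11 and 16). The test follows: "For this, an ANOVA of repeated measures or the Friedman test will be used", chosen by normality. A MANOVA is added, without saying whether the four occasions enter it jointly.
- **Analysis of data, last lines.** "Intention-to-treat analysis will be performed", with no definition of the term and no rule for missing scores. Just before it, after a sentence on inconsistencies and outliers, stands "Likewise, if necessary, statistical adjustments will be made".
- **Data Collection Procedures (Assessment Protocols).** Missed tests are expected: "If for any reason a participant cannot take the test due to any circumstance", with absence, discomfort, bruises and injury among the reasons, "his replacement will be arranged with IUEFD student with experience as soccer players" or with club trialists "who are not part of the comparison groups". Tests are fixed to Wednesday mornings. Training sessions have a next-day fallback (Interventions), but no make-up day is given for a FOCOS test.
- **Sample Size Calculation.** "Scenario 3 (90% power): (24 soccer players. GE = 12 and GC = 12" is the scenario adopted, with no allowance for losses.

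**The concern.** The substitute completes the four-a-side team, not the data set. The absent player has no IE for that week, and the named tests then also lose the scores he did provide. The adjustment sentence names no method. If a test is missed, a statistician following the text must either drop a randomised player or choose a method not written down beforehand.

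With 24 players, each lost row counts. The loss is avoidable where different players miss different tests, because most of their scores exist and would be thrown away. If misses follow injury or attendance, and these differ between groups, the players left could also cease to be comparable.

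The point covers the IE outcomes only. The MANOVA is affected only if all four occasions enter it together.

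**Working it through.** **1. The plan's own figure.** Sample Size Calculation gives a difference of 1.13 and an SD of 0.81, so d = 1.13/0.81 = 1.395. For a two-sample t test, two-sided 0.05, 12 per group, the noncentrality is 1.395 × √(12/2) = 3.42 on 22 df, and power is 0.904. The same calculation gives 10, 11, 12, 15 and 20 per group for the five scenarios, matching the plan.

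**2. What the named tests do with a gap.** On simulated data for 24 players and four tests, with one of 96 scores missing, a classical repeated-measures ANOVA routine refused to run. The Friedman test gave no result until the player was removed, leaving 23.

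**3. Scores lost.** Assumptions: all 24 took the pretest, and a fraction p misses each of the three later tests, independently.

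| Quantity | p = 2% | p = 5% | p = 10% |
|---|---|---|---|
| Complete players, 24(1−p)³ | 22.6 | 20.6 | 17.5 |
| Scores observed, 24[1+3(1−p)] | 94.6 | 92.4 | 88.8 |
| Scores used, 96(1−p)³ | 90.4 | 82.3 | 70.0 |
| Observed but discarded | 4.2 | 10.1 | 18.8 |
| Of these post-baseline, 72[(1−p)−(1−p)³] | 2.8 | 6.7 | 12.3 |
| Chance of any incomplete player, 1−(1−p)⁷² | 0.767 | 0.975 | 0.9995 |

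**4. Power, group-by-week test.** Assumptions: equal correlation ρ between tests, and a group difference of 0, 1/3, 2/3 and 1 times its week-16 value. The squared deviations of these weights from their mean sum to 5/9. Setting d²/(1−ρ) = 4.51 gives noncentrality (12×12/24) × (5/9) × 4.51 = 15.03 and power 0.90 on 3 and 66 df with no misses. The corresponding week-16 d is 1.78, 1.50 or 1.16 for ρ = 0.3, 0.5 or 0.7. Power is averaged over binomial numbers of complete players (complete-case) or over simulated miss patterns using all within-player information (all scores).

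| Independent misses | 2% | 5% | 10% |
|---|---|---|---|
| Complete-case | 0.876 | 0.834 | 0.750 |
| All scores, random player effect | 0.894 | 0.885 | 0.869 |
| Avoidable loss | 0.018 | 0.051 | 0.119 |

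As a cross-check, the plan's own t test at one time point gives 0.882, 0.844 and 0.766 complete-case, against 0.897, 0.886 and 0.865 using everyone tested then: about 1.5, 4 and 10 points.

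**5. The opposite pattern.** If the same players miss all three later tests, 24(1−p) = 23.5, 22.8 or 21.6 are complete. Only 24p = 0.5, 1.2 or 2.4 pretest scores are discarded. The chance of any incomplete player is 1−(1−p)²⁴ = 0.384, 0.708 or 0.920. Power on the group-by-week test is 0.892, 0.880 or 0.857 by either route, so the avoidable loss is about nil.

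**6. Choice of covariance.** With complete data, an unstructured covariance turns the group-by-week test into a Hotelling-type F on 3 and 24−4 = 20 df. At noncentrality 15.03 its power is 0.851, against 0.900. Under the pattern in step 5 it is 0.840, 0.823 or 0.791, against 0.892, 0.880 or 0.857. The gains in step 4 therefore belong to the random-player-effect model.

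**The case against.** Four objections deserve weight.

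- **Nothing may be missed.** The size rests wholly on assumed rates, and the listed reasons mix brief ones with injury, so neither miss pattern is established. This stands. The range runs from nil to about 12 points. But the plan itself expects missed tests, and even at 2% per test the chance of at least one incomplete player is 38% to 77%.
- **A reader might infer that the plan contradicts its own intention-to-treat statement.** The documents do not support that. The term is undefined. Read as analysing players in their assigned groups, it is compatible with complete cases. Read as including everyone, it implies a method that has not been named. The defect is under-specification.
- **A reader might infer a biased comparison, or that substitutes' scores will stand in for absent players.** Neither is shown. Nothing says misses will differ by group. The scoring text refers to coded participants, and the substitutes come from outside the two groups, although an explicit exclusion would be safer.
- **The power figures illustrate a test the plan does not spell out.** This also stands. The plan names no group-by-week term, the Friedman test has no group factor, and the 1.13 and 0.81 are not tied to an IE. The figures indicate scale only.

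It is also tempting to prescribe an unstructured covariance as the main model. On the assumptions in step 4 that costs about 5 points with no misses and 5 to 7 when the same players miss all later tests, so the quoted gains cannot be claimed for it.

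**Conclusion.** The gap is real and should be closed. As written, the IE analysis would be complete-case whenever a FOCOS test is missed and the named tests are run in standard form, and nothing else in the plan supplies a method.

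The avoidable power loss is about 2, 5 or 12 points at assumed independent miss rates of 2%, 5% or 10%, given equal correlation and a linearly growing effect. It is about nil if the same players miss every later test. I am confident about the gap. Its size is conditional on rates that the documents do not give.

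**What to change.** In Analysis of data, replace ANOVA/Friedman as the main analysis of each IE with a likelihood-based linear mixed model:

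- fixed effects for group, week and group-by-week, a random player effect, and Kenward-Roger degrees of freedom;
- every available FOCOS score, pretest included as an outcome, of every randomised player in the assigned group.

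Also:

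- state that substitutes' scores are not analysed;
- state the missing-at-random assumption;
- report missed tests by group and week;
- give an unstructured covariance as a sensitivity analysis only, since it protects against unequal correlations at the power cost shown above.

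With complete data the random-player-effect model generally gives the same group-by-week test as the uncorrected repeated-measures ANOVA, so nothing is lost if no test is missed.

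The cost is a short edit and a little more work in R, which the plan already names, with no extra players or visits. Two downsides should be acknowledged: missing at random cannot be verified, and the random player effect assumes equal correlation between tests.
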